4.3 Multiple Imputation Under MAR

For the discontinued subjects, alternative to the J2R method, the annualized rate of VOCs after dropout will be imputed using multiple imputation under MAR. MAR assumes the missing value is independent of unobserved outcomes given observed data (i.e., annualized rate of VOCs after dropout can be modeled based on subjects with observed annualized rate of VOCs).

The following steps will be implemented:

Step 1:

A fully conditional specification (FCS) method will be used to impute the missing annualized rate of VOCs after dropout using a regression model. The regression will include the covariates of treatment, observed number of VOCs, duration in the study, region (North America/Europe vs. Africa/Middle East) and HU use (Yes vs. No). Missing data imputation will be performed using the SAS PROC MI procedure. Refer to [Appendix 6](#) for the order of variables in the model.

Step 2:

For each of the repetitions in the datasets, the total number of VOCs for the entire study will be recalculated for the dropouts as:

$$[\text{Total number of observed VOCs during treatment period} + \text{annualized rate of VOCs after dropout} * (\text{Date of expected last study drug if not discontinued} - \text{Date of last dose of study drug} + 1)]/365.25$$

Step 3:

The negative binomial regression (or Poisson regression as appropriate) with total number of VOCs as dependent variable, log treatment exposure as an offset, stratification factors and treatment as independent variables will be run for each of the 100 datasets to obtain 100 estimators of interest.

Step 4:

Use SAS PROC MIANALYZE to produce an overall pooled estimate (mean of 100 estimates)

The multiple imputation sample code is specified in [Appendix 6](#). However, there could be certain adjustments due to unexpected data issues after unblinding treatment. All post-unblinding modifications to the multiple imputation model or approaches to address missing data will be described in the CSR.

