10.5 Windowing Conventions

All scheduled study visits are defined relative to Study Day 1, the date of first dose. Scheduled visit windows are defined in [Appendix 3](#). A windowing convention will be used to determine the analysis visit value for a given measurement and will be applicable for all by-visit summaries and analyses for efficacy and safety data. Refer to [Table 2](#) below for specific visit windows.

Table 2 Visit Windows for Efficacy and Safety Analyses

| For all Efficacy (Except for QoL) and PD Analyses | |
|---|--|
| Scheduled Study Visit (Protocol Scheduled Day) | Analysis Visit Window (Study Day) |
| Baseline | ≤ 1 |
| Week 4 (Day 28 ± 5) | 2 to 43 |
| Week 8 (Day 56 ± 5) | 44 to 71 |
| Week 12 (Day 84 ± 5) | 72 to 99 |
| Week 16 (Day 112 ± 7) | 100 to 141 |
| Week 24 (Day 168 ± 7) | 142 to 211 |
| Week 36 (Day 252 ± 7) | 212 to 309 |
| Week 52 (Day 364 ± 7) | ≥ 310 |
| For QoL Analysis | |
| Scheduled Study Visit (Protocol Scheduled Day) | Analysis Visit Window (Study Day) |
| Baseline | ≤ 1 |
| Week 4 (Day 28 ± 5) | 2 to 57 |
| Week 12 (Day 84 ± 5) | 58 to 127 |
| Week 24 (Day 168 ± 7) | 128 to 211 |
| Week 36 (Day 252 ± 7) | 212 to 309 |
| Week 52 (Day 364 ± 7) | ≥ 310 |
| For Safety Analysis | |
| Scheduled Study Visit (Protocol Scheduled Day) | Analysis Visit Window (Study Day) |
| Baseline | ≤ 1 |
| Week 1 (Day 7 ± 2) | 2 to 15 |
| Week 4 (Day 28 ± 5) | 16 to 43 |
| Week 8 (Day 56 ± 5) | 44 to 71 |
| Week 12 (Day 84 ± 5) | 72 to 99 |
| Week 16 (Day 112 ± 7) | 100 to 127 |
| Week 20 (Day 140 ± 7) | 128 to 155 |
| Week 24 (Day 168 ± 7) | 156 to 190 |
| Week 30 (Day 210 ± 7) | 191 to 232 |
| Week 36 (Day 252 ± 7) | 233 to 274 |
| Week 44 (Day 308 ± 7) | 275 to 337 |

| For Safety Analysis | |
|---|--|
| Scheduled Study Visit (Protocol Scheduled Day) | Analysis Visit Window (Study Day) |
| Week 52 (Day 364 ± 7) | 338 to 379 |
| Week 56 (Day 392 ± 7) | ≥ 380 |

Windowing will be applied prior to any missing data calculations. The last non-missing measurement taken prior to the date of first dose (including unscheduled assessments) will be labeled as “Baseline”. Unscheduled or Screening visits that occurred before the baseline visit will not be assigned an analysis visit. The early discontinuation visit will be eligible for allocation to an analysis visit.

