13.5.2.1 Derivation of Annualized Rate of VOCs

As described in Protocol Inclusion Criterion 3, a VOC is defined as a documented episode of acute painful crisis (for which there was not an explanation other than VOC) that involves moderate to severe pain lasting for at least 2 hours and at least one of the following:

- Use of escalated analgesia (including healthcare professional-instructed use of an analgesic prescription)
- A hospital, emergency department, or clinic visit and/or healthcare telephone consultation at the time of occurrence
- Diagnosis of acute chest syndrome (ACS) (defined as an acute illness characterized by fever and/or respiratory symptoms, accompanied by a new pulmonary infiltrate on a chest X-ray), hepatic sequestration, or splenic sequestration, or priapism (in males)

VOCs collected during the study are assumed to meet these criteria as well.

VOC information, including start and end date/time, primary setting for treatment (hospitalization/ emergency department, etc.), and treatments are collected on the "VOC" CRF page.

Annualized rate of VOCs is calculated as Total number of VOCs / ([Date of last dose of study drug– date of first dose of study drug + 1]/365.25).

Date of last dose of study drug is collected from the "End of Treatment" CRF page. If that date is not available (which is expected for some of the subjects in the IA), the data cut-off date will be used.

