Appendix 6 SAS Codes for Statistical Analysis

| Test | Template SAS Code for Modeling (SAS Version 9.4) |
|--|--|
| Determination of lower O'Brien-Fleming stopping boundary for the primary efficacy endpoint at the interim analysis | Proc Seqdesign errspend plots=all boundaryscale=pvalue; PrimaryEfficacy: design alpha = 0.05 beta = 0.20 alt = twosided /* two-sided test*/ nstages = 2 method (reject)= errfuncobf /* O'Brien-Fleming as implemented by Lan-DeMets */ info = cum(24 52) /* information proportion are based on 24 wks out of 52 wks*/; run; |
| Primary Analysis: Stratified Wilcoxon rank-sum test | proc npar1way data=ITT; Title 'Primary Endpoint – Comparison of Annualized VOC Rates'; Title2 'Intent To Treat Population'; class TRT; var ARVOC; strata <stratification factors: REGION HU >; run; |
| Negative binomial regression | proc genmod data=ITT; Title 'Sensitivity Analysis for Primary Endpoint – Negative Binomial Regression'; class TRT <stratification factors: REGION HU >; /*TRT is treatment group; model Y = TRT <stratification factors: REGION HU> / dist = negbin link = log offset = LTIME; /*Y is the count of VOC, LTIME is the log of exposure time in years; lsmeans TRT / cl diff exp; |
| Time to Event Analysis | proc lifetest data=ITT plots=(survival(nocensor atrisk cb)); Title 'Secondary Endpoint – Time to Event Analysis Time to first VOC'; time TIME*VOC(0); Strat TRT; run; |
| Mixed model repeated measures (MMRM) | proc mixed data=ITT; class SUBJECT TRT VISIT HU REGION; model CFB = TRT VISIT TRT*VISIT BASELINE HU REGION; /*CFB=change from baseline; repeated VISIT/ TYPE = UN ddfm=kr sub=SUBJECT; /*Type=CS and then Type AR(1) will be used if UN does not work*/ lsmeans TRT*VISIT/cl diff alpha=0.05; lsmeans TRT/cl diff alpha=0.05; run; |
| Multiple Imputation for the annualized rate of VOCs | proc mi; class TRT REGION HU ; fcs reg(AVOC = TRT REGION HU VOC_O DUR); /*AVOC= annualized VOC rate; VOC_O =Number of observed VOCs; DUR = Duration in the study. run; |

| Test | Template SAS Code for Modeling (SAS Version 9.4) |
|--|---|
| with FCS Method | |
| Negative binomial regression based on Multiple Imputed dataset | <pre>proc genmod data=MIDATA; by _imputation_; class TRT REGION HU ; /*TRT is treatment group; model Y = TRT REGION HU / dist = negbin link = log offset = LTIME; *Y is the count of VOC, LTIME is the log of exposure time in years; lsmeans TRT / cl diff exp; run;</pre> |

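### The multiple-imputation sensitivity analysis regresses the VOC rate on the count and duration it is built from, so imputed post-dropout rates are mis-scaled and the treatment difference is diluted

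*SAP*

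**What the plan says.** SAP section 13.5.2.4 lists sensitivity analyses for the primary endpoint. Item 4.3 is a multiple imputation under MAR with 100 imputed datasets. In Step 1, "A fully conditional specification (FCS) method will be used to impute the missing annualized rate of VOCs after dropout using a regression model". On the predictors: "The regression will include the covariates of treatment, observed number of VOCs, duration in the study, region" and HU use. The Appendix 6 template gives the model as "fcs reg(AVOC = TRT REGION HU VOC_O DUR", with the key "AVOC= annualized VOC rate; VOC_O =Number of observed VOCs; DUR = Duration in the study".

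The outcome is defined in section 13.5.2.1: "Annualized rate of VOCs is calculated as Total number of VOCs", divided by the time from first to last dose in years of 365.25 days.

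On who supplies the fit, item 4.3 says only that "annualized rate of VOCs after dropout can be modeled based on subjects with observed annualized rate of VOCs". It does not say whether these are completers alone. It also does not say whether DUR is treatment or study duration, or whether the Step 3 exposure offset for a dropout is actual exposure or 52 weeks.

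**The concern.** In anyone whose rate is observed, the count is the numerator of the outcome and, if DUR means treatment duration, DUR is the denominator. A linear regression on both reproduces the definition of the rate. It does not learn how VOC rates vary between patients or arms.

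Two consequences follow for dropouts.

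- A relation that holds when the count covers a full year is applied to a count that covers part of one.
- Because count and duration already explain the outcome, the treatment coefficient is about zero, so the arm difference enters the imputed rates only through the truncated counts.

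The SAP plans for 25% dropout (section 8.1.2). A check labelled MAR should return the treatment effect without dilution when data really are missing at random. Otherwise, a weaker result in item 4.3 could be read as sensitivity to dropout when it comes from the imputation model.

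**Working it through.** **The plan's own figure.** Item 4.3 states none. The nearest is the power in section 8.1.2 (SD 2.7, two-sided 0.05, 49 v 31 and 37 v 24). Multiplying group sizes by 3/π and using the noncentral t gives 0.876 (difference 2.0) or 0.886 (2.034) against the stated 0.880. With dropout it gives 0.775 or 0.788 against 0.776. The planning inputs reproduce.

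**Inputs.** From the SAP: 31 placebo and 49 higher-dose subjects, 5 v 3 VOCs a year, 25% dropout, last treatment visit at day 364 ± 7 (section 10.5). Assumed: random dropout at uniform times, and gamma-Poisson dispersion 0.3, with 0.1-0.5 as the range. The SAP's SD of 2.7 implies (2.7² - 5)/5² = 0.09 at mean 5 and (2.7² - 3)/3² = 0.48 at mean 3.

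**By hand, completer fit, DUR = treatment days.** The outcome is 365.25 × v/d, for count v and days d. Linearise at d = 364:

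- Slope on count: 365.25/364 = 1.003.
- Mean count in completers: (31×5 + 49×3)/80 = 3.775 a year, times 364/365.25 = 3.762. Slope on duration: -3.762 × 365.25/364² = -0.0104 per day.
- What remains is the count-by-duration product. With durations spread evenly over ±7 days (SD 14/√12 = 4.04) and a rate SD of 3.0, residual SD = 3.0 × 4.04 × 365.25/364² = 0.033. R-squared = 1 - (0.033/3.0)² = 0.9999.
- Imputed rate for an average dropout at day 182: placebo v = 5×182/365.25 = 2.49, giving 1.003×2.49 + 0.0104×182 = 4.39. Higher dose v = 1.495, giving 1.50 + 1.89 = 3.39.

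The imputed arm difference is 1.0 where the truth is 2.0. It equals the true difference times the fraction of the year observed, so earlier dropouts are diluted more.

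**By simulation.** This used 1,000-1,500 trials per scenario, 20 imputations, regression draws as in PROC MI, then negative binomial regression and Rubin's rules. The completer fit gave R-squared 0.9999, residual SD 0.03 (rate SD 3.0), count slope 1.003, duration slope -0.010 a day and a mean treatment coefficient of 0.0001. Imputed rates averaged about 4.35 v 3.35. Without count and duration, R-squared was about 0.14.

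Results at 25% dropout and dispersion 0.3, true log rate ratio -0.511, with Step 2 units corrected and a 52-week offset:

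| Analysis | Mean log rate ratio | Mean SE | Between-imputation share |
|---|---|---|---|
| No dropout | -0.506 | 0.168 | n/a |
| Observed-data negative binomial | -0.506 | 0.177 | n/a |
| SAP item 4.3 | -0.464 | 0.162 | 0.2% |
| Negative binomial count imputation | -0.505 | 0.177 | 9.5% |

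The Monte Carlo error of -0.464 is 0.171/√1500 = 0.004, so the shift is not noise. As rate ratios, exp(-0.464) = 0.63 against exp(-0.511) = 0.60. At 40% dropout the item 4.3 estimate is -0.438.

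**Other readings of the SAP (25% dropout).**

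| Reading | R-squared | SE v observed-data | Also |
|---|---|---|---|
| Main, as above | 0.9999 | -9% | -13% to -14% at 40% dropout |
| Dropouts' on-treatment rates also in the fit | 0.87 | -3% | draw SD 1.3; log rate ratio -0.476; arm gap in imputed rates about 1.2 |
| DUR = study duration, some completers with 4-week follow-up | 0.9997 | +4% | mean imputed rate 2.06 v true 3.78 |
| Step 2 formula taken literally | 0.9999 | +1% | log rate ratio -0.458 |

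With actual exposure as the Step 3 offset, the SE is 0.194. That is above the observed-data SE but only 0.87 of the estimator's own spread, and 95% coverage is 0.90-0.91.

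**The case against.** The strongest counter-argument is that a reader might infer the standard error is simply too small and the confidence interval too narrow. The documents and the checks do not support that as a general statement.

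- In the main reading the estimator's own spread shrinks along with its SE. SE over empirical SD is 0.945, against 0.953 for the observed-data analysis, and coverage under no effect is 0.934 against 0.933.
- Across readings with a 52-week offset, the SE runs from 14% below to 4% above the observed-data SE.
- The clear under-coverage arises with the actual-exposure offset. There the SE is also too small for the estimator's spread (ratio 0.85) when dropouts' rates enter the fit, so the problem lies in Step 3 more than in Step 1.

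A reader might also call the procedure single imputation in all but name. That holds for the completer fit, but the SAP does not restrict the fit to completers, and section 13.5.2.3 treats the endpoint as never missing. If dropouts' on-treatment rates enter, R-squared is about 0.85-0.90 and the draws vary materially. Likewise, DUR is described as time in the study, so it is the denominator only if that means treatment time. For a dropout, the observed count is not the numerator of the post-dropout rate at all.

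Finally, this is not the only MAR-type check. Item 2 of the same section, negative binomial regression of observed counts with a log-exposure offset, already relies on that assumption. Items 4.1 and 4.2 probe dropout in other ways.

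These points limit the claim and its importance. They do not remove the dilution of the arm difference, which appears with the completer fit and with the wider fit.

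**Conclusion.** Step 1 and its Appendix 6 code give a poor imputation model as specified: it predicts a rate from the components of that rate. With a completer fit, the treatment coefficient is about zero, the between-imputation share of variance is about 0.1-0.5% (8-15% for count imputation), and a duration slope learned over about two weeks of variation is extrapolated over months. The log rate ratio is pulled about 9% toward zero at 25% dropout. With a wider fit the near-determinism goes, but some dilution stays.

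The sizes rest on assumed dispersion, random dropout at uniform times, a two-arm comparison and corrected Step 2-3 arithmetic. The structural point needs none of these. An SE about 9% below observed-data belongs to the main reading only and should be given with its range.

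The consequence is confined to one sensitivity analysis that carries no alpha. The primary Wilcoxon test and item 2 are untouched. It is worth correcting before unblinding, because item 4.3 already allows post-unblinding changes to the imputation model.

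**What to change.** Replace Step 1 and the PROC MI template with imputation of counts:

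1. Fit the negative binomial model to observed counts with treatment, region and HU use, and log exposure as offset.
2. Draw the model parameters for each imputation.
3. For each dropout, draw the VOC count over the unobserved days from the predictive distribution given that subject's observed count and exposure.
4. Analyse observed plus drawn counts with a full-period (52-week) offset, and combine with Rubin's rules.

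State the offset explicitly. Correct the Step 2 expression too: its closing division by 365.25 applies to the observed count as well as to the rate-times-days term. Correcting Step 2 alone would not cure Step 1.

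The cost is SAP wording and programming. In the check above this version gave -0.505 against a true -0.511. Its result should lie close to item 2, since both rest on the same model, so it should be presented as a consistent MAR analysis and not as independent evidence of robustness.

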13.5.2.5 Supplementary Analysis for Primary Efficacy Analyses

13.5.3 Subgroup analyses will be performed as supplementary analyses and detailed in [Section 13.5.6.Key Secondary Efficacy Analysis](#)

13.5.3.1 Time to first VOC

The time to first VOC event will be analyzed using Kaplan-Meier methods. Time in months to the first VOC event can be calculated as $([\text{date of first VOC event} - \text{date of first dose} + 1] / 30.4375)$.

Both start and end date of VOC event will be collected from “VOC” CRF page. The start date of the VOC is not expected to be missing and will be used for the analysis. In the rare event the start date is missing, then the end date can be used. If both start date and end date are missing, no imputation will be made and the event will be excluded from the analysis.

Subjects who experience no VOC events during the study will be censored at their study end date (or date cut-off date if the study end date is not available). Using the ITT set, the number and percentage of subjects with events (subjects who experienced at least 1 VOC on-study) and censored (subjects who did not experience any VOCs on-study) will be presented. The 25th, 50th (median), and 75th percentiles, along

with associated 2-sided 95% CIs based on the Brookmeyer and Crowley method will be presented. The p-values from a stratified log rank test and hazard ratios (and 95% CIs) estimated from a stratified Cox regression model with treatment arm and stratification factors (region and HU use) as covariates will be presented for comparison of each treatment group to placebo. Kaplan-Meier curves will be produced for the time to first VOC with separate curves for each treatment group.

Sensitivity analysis will be performed for Time to first VOC using the mITT and PP analysis sets. Major protocol deviations and subjects (or data) excluded from the PP analysis set will be defined by the Sponsor in a blinded manner prior to database lock. No imputation will be performed for the PP analysis.

13.5.3.2 Other sensitivity analyses may be added. All sensitivity analyses will be performed at FA.HbF responder rate at Week 24

13.5.3.2.1 Analysis and Imputation Methods

HbF responder rate (as defined by the proportion of subjects with an absolute increase of $\geq 3\%$ from baseline) at Week 24 will be assessed using a stratified Cochran-Mantel-Haenszel (CMH) test adjusted for stratification factors of region (North America/Europe vs. Africa/Middle East) and HU use (Yes vs. No). The ITT set will be used for this analysis.

The frequency and percentage of responders and non-responders at Week 24 will be presented for each treatment group as well as ORs, RRs, 95% Cis, and p-values from the CMH test comparing active groups to placebo.

Bar plots will be provided, and the proportion of subjects with response in HbF in each treatment group, Odds ratios, 95% CI, and p values will be displayed for each treatment comparison.

The following imputation rules will be applied for the key secondary efficacy endpoint (HbF responder at Week 24):

1. Subject will be treated as a non-responder if there is an initiation of HU post randomization and prior to Week 24.
2. If HbF value is missing at Week 24, the HbF value at Week 16 will be used for the analysis. If HbF value at Week 16 is also missing, subject will be treated as a non-responder.
3. Any HbF value within 8 weeks (56 days) of a RBC transfusion will be excluded from all analyses. If the subject does not have a valid HbF value at Week 24 and/or Week 16, subject will be treated as a non-responder.

Number of subjects with imputed values for the key secondary efficacy endpoint and the reason for imputation (imputed as non-responder because of initiation of HU post randomization, imputed with Week 16 value because of Week 24 value is missing, imputed from the last post-baseline assessment prior to RBC transfusion) will also be summarized. The observed and imputed Week 24 HbF values will both be summarized for the by-visit analysis.

